8.6 Follow up Period

8.6.1 Visit 6 (day 182 \pm 14 days)

Subjects will be asked to return to site for follow up Visit 6, 168 to 196 days (6 months) after Visit 1.

Blood samples will be collected for immunogenicity assessments (Chikungunya antibody ELISA and PRNT₅₀). For details on laboratory sampling and testing, see section 8.11.

The subjects are invited to return to study site for the final Visit 7 on study day 365 (\pm 14 days).

8.6.2 Visit 7 (day 365 \pm 14 days), termination visit

Subjects will be asked to return for the final Visit 7, 351 to 379 days (1 year) after Visit 1.

Blood samples will be collected for immunogenicity assessments (Chikungunya antibody ELISA and PRNT₅₀) and for isolation of serum for passive transfer. For details on laboratory sampling and testing, see section 8.11.

8.7 Early Termination Visit (ET)

Subjects who are withdrawn or wish to discontinue the study prematurely for any reason shall be asked to attend an early termination visit.

If the early termination occurs within the treatment period (at or before Visit 5), subjects shall perform all procedures as defined for Visit 5. If the early termination occurs within the follow up period (after Visit 5), subjects shall perform all procedures defined for Visit 7.

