5.2 Secondary Objectives

- To compare immunogenicity, safety and tolerability between different doses and formulations of MV-CHIK during the treatment period up to day 56
- To investigate the immunogenicity and safety of a novel liquid vaccine formulation

To cover this objective immunogenicity will be determined by means of PRNT₅₀ at the following timepoints during the treatment period: Visit 1 (day 0), Visit 3 (day 28) and Visit 5 (day 56). Solicited and unsolicited AEs will be recorded at each visit during the treatment period.

- To evaluate cellular responses induced by one or two immunisations

The cellular response will be investigated by T cell analysis of PBMCs isolated at Visit 1(day 0), Visit 2 (day 14), Visit 3 (day 28), Visit 4 (day 42) and Visit 5 (day 56)

- To evaluate the long-term immunogenicity of MV-CHIK up to one year after the first MV-CHIK treatment.

The long-term immunogenicity will be observed by means of PRNT₅₀ detecting anti-Chikungunya antibodies 6 months and one year after the first treatment with MV-CHIK (at Visit 6 and Visit 7).

- To collect human sera for future efficacy evaluation, by passive transfer of anti-Chikungunya antibodies to virus susceptible non-human primates

On study day 0 (Visit 1), day 28 (Visit 3), day 56 (Visit 5) and day 365 (Visit 7) blood samples will be collected for isolation of anti-Chikungunya antibody containing human serum.

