6.4 Study Flowchart

6.5 Study Procedures

Table 2: Study Procedures

Visit	Screening	Treatment Period					Follow up Period		ET
		V1	V2	V3	V4	V5	V6	V7	
Study Day	-28 to -1	0	14 ±1	28 ±5	42 ±5	56 ±5	182 ±14	365 ±14	(7)
Informed Consent	X								
Inclusion/Exclusion Criteria	X	X							
Medical History	X	X							
Vaccination History	X								
Vital Signs (1)	X	X		X			X		X
Physical Examination (2)	X	X		X			X		X
Adverse Events (3)		X	X	X	X	X			X
Concomitant Medication (4)	X	X	X	X	X	X			X
Clinical Laboratory (5)	X			X			X		X
Pregnancy Test	X	X		X			X		X
Study Treatment (8)		X		X					
Dispense subject diary		X		X					
Collect subject diary			X		X				X
Local Tolerability (6)		X	X	X	X	X			X
Immunogenicity (PRNT ₅₀)		X		X		X	X	X	X
T-cell Immunity		X	X	X	X	X			X
CHIKV-antibodies (ELISA)		X		X		X	X	X	X
Measles-antibodies (ELISA)		X		X		X			X
Serum collection for passive transfer		X		X		X		X	X

(1) Assessment of vital signs will include systolic and diastolic blood pressure, pulse rate and body temperature

(2) A full physical examination will be performed at screening and a system based physical examination will be done at Visit 1, 3 and 5, if necessary according to findings in a symptom-directed physical examination

(3) Conditions/symptoms noted prior to first IMP administration will be reported as medical history and not as AEs, At Visit 6 and 7 AEs will not be recorded as subjects are allowed to participate in other clinical studies during the follow-up period.

(4) Medications administered within 30 days prior to screening until end of treatment period will be documented as concomitant medication.

(5) Clinical Laboratory parameters include:

- Virology: HB s-Ag, anti-HB c-Ab, anti-HC-Ab, HIV-Ab (only once at screening)
- Haematology: haemoglobin, haematocrit, erythrocyte count, differential and total white blood count, platelets
- Chemistry: creatinine, potassium, sodium, calcium, AST, ALT, alkaline phosphatase, bilirubin
- Coagulation parameter: prothrombin time (PT), activated partial thromboplastin time (aPTT), fibrinogen
- Urinalysis: pH-value, glucose, protein, bilirubin, urobilinogen, blood, leucocytes esterase, nitrite, ketone and specific gravity. In case of abnormal findings, a microscopy will be done for confirmation.

Please refer to section 8.11.1

(6) Local tolerability to be investigated 2 hours after each vaccination and additionally at the subsequent visits and prior to IMP administration.

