8.5.5 Visit 5 (day 56 \pm 5 days)

Subjects will be asked to return to site for Visit 5, 51 to 61 days after Visit 1.

The investigator or designee will examine and document local tolerability (of the previous vaccination site) and ask about any new concomitant medications or AEs occurred since the last visit.

Symptom-directed physical examination, system-based assessment (only if necessary according to findings in symptom-directed physical exam) and vital signs (systolic and diastolic blood pressure, pulse rate and body temperature) will be recorded. A serum pregnancy test will be performed in all women.

Blood samples will be taken for clinical chemistry, haematology, coagulation parameters and urine samples will be collected for urinalysis.

Additionally, blood samples for immunogenicity assessments (measles and Chikungunya ELISA, PRNT₅₀) and isolation of serum for passive transfer will be drawn from an appropriate

vein. For T-cell assays blood samples will be collected and PBMCs will be prepared. For details on laboratory sampling and testing, see section 8.11.

Upon Visit 5, the treatment period of this study will be completed. Subjects will be allowed to participate in other clinical trials after all procedures of Visit 5 will have been performed.

Blood pressure and pulse rate will be measured before participants will be discharged, and subjects are invited to return to study site for follow up Visit 6 on study day 182 (\pm 14 days).

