8.9 Discontinuation/Withdrawal of Subjects

Subjects may withdraw from participation in the study at any time. If a subject withdraws or is withdrawn prior to completion of the study, the reason for this decision should be recorded in the electronic case report forms (eCRFs) although it is recognised that the subject may refuse to provide a reason.

Generally, any enrolled/vaccinated subject may withdraw or be withdrawn from the study for the following reasons:

- The subject withdraws consent
- The subject fails to comply with the requirements of the protocol
- At the discretion of the investigator
- For an adverse event, which at the discretion of the investigator requires discontinuation of the subject or results in inability to continue to comply with trial procedures
- if the administration of a drug, which is not permitted by the study protocol, becomes necessary (this should be discussed and agreed between the investigator and the sponsor)
- violation of exclusion criteria 1, 4, 5, 7, 12, 15, 16, 17, 18, 19 or 20 during the study (this should be discussed and agreed between the investigator and the sponsor)

All subjects who withdraw or are withdrawn prematurely from the study will undergo an early termination visit (see section 8.7).

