Irrespective of the stopping rules the study may be temporarily suspended or prematurely terminated at any time if there is sufficient reasonable cause, and if agreed to by both the investigator and the sponsor as being in the best interests of subjects and justified on either medical or ethical grounds. In terminating the study, the sponsor, the CRO, and the investigator will ensure that adequate consideration is given to the protection of the subjects' interests.

Whenever the study is stopped the competent authorities and ethical committees will be informed.

In case the entire study has to be discontinued prematurely, all concerned subjects should be asked to perform an early termination visit.

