8.11.3 Serum Samples for Passive Transfer

At Visit 1, a volume of 50 ml and at Visit 3, 5 and 7, a volume of 200 ml blood will be collected for isolation of human serum and frozen at -80°C for future efficacy evaluation of the MV-CHIK vaccine. Sera of different anti-Chikungunya antibody titres will be transferred to non-human primates to investigate protective potential against Chikungunya virus challenge.

Table 3: Blood Sample Collection

Test	Type of Vials	Volume ml	Visits	Total Volume ml
Virology (HIV, HBV, HCV)	serum	* 0	VS	* 0
β-HCG Pregnancy Test	serum	*0, 1x 3-5	VS, V1, V3, V5	3-5
Haematology	EDTA	3 - 5	VS, V3, V5	9-15
Coagulation	citrate tubes	3 - 5	VS, V3, V5	9-15
Clinical Chemistry	serum	8 - 10	VS, V3, V5	24-30
PRNT ₅₀	serum	8 - 10	V1, V3, V5, V6, V7	40-50
ELISA CHIKV	serum	8 - 10	V1, V3, V5, V6, V7	40-50
ELISA Measles	serum	** 0	V1, V3, V5	** 0
PBMCs for T-cell Analysis	citrate tubes	24-30	V1, V2, V3, V4, V5	120-150
Passive Transfer	serum	50 + 3x 200	V1, V3, V5, V7	650
				895-965

* 0 ml: Virology testing at screening and pregnancy testing at screening, V3 and V5 will be performed from the same sample as Clinical Chemistry, no additional blood draw will be necessary

** 0 ml: ELISA for determination of Measles antibodies will be performed from the same sample as the ELISA for CHIK-Ab, no additional blood draw will be necessary

Total blood volume collected during the entire study duration of one year will be 895-965 ml

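### Early termination repeats the 200 ml passive-transfer draw with no minimum interval since the previous one, and the sections that define that draw do not mention the early-termination visit

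*Combined protocol and SAP*

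**What the plan says.** Protocol 8.7 defines the ET visit by reference to scheduled visits. For the treatment period: "If the early termination occurs within the treatment period (at or before Visit 5), subjects shall perform all procedures as defined for Visit 5". For follow-up: "If the early termination occurs within the follow up period (after Visit 5), subjects shall perform all procedures defined for Visit 7". Footnote 7 to Table 2 (protocol 6.5) repeats the rule, as does footnote 7 in SAP 1.6. The row of Table 2 labelled "Serum collection for passive transfer" is marked at Visits 1, 3, 5 and 7 and also in the ET column.

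The passive-transfer draw is part of Visit 5. Protocol 8.5.5 reads: "Additionally, blood samples for immunogenicity assessments (measles and Chikungunya ELISA, PRNT₅₀) and isolation of serum for passive transfer will be drawn from an appropriate" vein. Section 8.6.2 includes it at Visit 7 as well. The volume is in 8.11.3: "At Visit 1, a volume of 50 ml and at Visit 3, 5 and 7, a volume of 200 ml blood will be collected".

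The sections that define this collection name scheduled visits only. The objective in 5.2 says: "On study day 0 (Visit 1), day 28 (Visit 3), day 56 (Visit 5) and day 365 (Visit 7) blood samples will be collected". Section 8.11.3 and Table 3 list the same four visits, and Table 3 has no ET entry for any sample type.

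On who attends, 8.9 states: "All subjects who withdraw or are withdrawn prematurely from the study will undergo an early termination visit". If the whole study is discontinued early, 8.9.1 says that "all concerned subjects should be asked to perform an early termination visit". Section 8.7 also words attendance as a request.

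**The concern.** The schedule spaces the 200 ml draws through its visit windows. An ET visit has no window: it can follow Visit 3 or Visit 5 by any number of days. Because 8.7 imports all procedures of the later visit, a subject who leaves soon after a 200 ml draw is due another one. Sections 8.7, 8.9 and 8.11.3 give no minimum interval, reduced volume or exemption.

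The second draw is for research only. Shortly after Visit 3 or Visit 5 it largely repeats serum just collected, and it falls on none of the planned collection days (0, 28, 56 and 365). No planned analysis depends on it: SAP section 5 only lists ET immunogenicity data, and SAP 5.2 leaves passive-transfer results out of its scope.

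A site also cannot look up how much blood an ET visit takes, because Table 3 does not say.

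**Working it through.** **Inputs, all from Table 3 (ml per visit):** haematology 3-5, coagulation 3-5 and clinical chemistry 8-10 (screening, V3, V5); PRNT50 8-10 and CHIKV ELISA 8-10 (V1, V3, V5, V6, V7); PBMC 24-30 (V1 to V5); a separate pregnancy-test tube 3-5 (V1 only); passive transfer 50 (V1) and 200 (V3, V5, V7). Virology, measles ELISA and the other pregnancy tests need no extra blood.

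**Step 1. Reproduce the stated total.**

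| Visit | Sum | ml |
|---|---|---|
| Screening | (3-5) + (3-5) + (8-10) | 14-20 |
| V1 | (3-5) + (8-10) + (8-10) + (24-30) + 50 | 93-105 |
| V2 | 24-30 | 24-30 |
| V3 | (3-5) + (3-5) + (8-10) + (8-10) + (8-10) + (24-30) + 200 | 254-270 |
| V4 | 24-30 | 24-30 |
| V5 | as V3 | 254-270 |
| V6 | (8-10) + (8-10) | 16-20 |
| V7 | (8-10) + (8-10) + 200 | 216-220 |
| Total | | 895-965 |

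This matches the protocol's 895-965 ml exactly.

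**Step 2. Volume at an ET visit under 8.7.**
- At or before Visit 5 (Visit 5 set): 254-270 ml. Without passive transfer: 54-70 ml.
- After Visit 5 (Visit 7 set): 216-220 ml. Without passive transfer: 16-20 ml.

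**Step 3. Add the preceding large visit.**
- ET days after Visit 3: (254-270) + (254-270) = 508-540 ml, of which 400 ml is passive transfer. Without the second passive-transfer draw: (254-270) + (54-70) = 308-340 ml.
- ET days after Visit 5: (254-270) + (216-220) = 470-490 ml. Without the second draw: (254-270) + (16-20) = 270-290 ml.

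**Step 4. Spacing in the ordinary schedule.** Visit 3 falls 23 to 33 days after Visit 1 (8.5.3) and Visit 5 falls 51 to 61 days after (8.5.5). The gap between their draws is nominally 28 days, at least 51 - 33 = 18 days and at most 61 - 23 = 38 days. Visit 7 falls at least 351 - 61 = 290 days after Visit 5. The shortest scheduled gap between two 200 ml draws is therefore 18 days. The ET rule has no such floor.

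**Step 5. Cumulative volume including the ET visit.**
- ET after Visit 3: (14-20) + (93-105) + (24-30) + (254-270) + (254-270) = 639-695 ml.
- ET after Visit 5: everything through Visit 5 (663-725) + (216-220) = 879-945 ml.
- ET after Visit 6: 895-965 ml, the same as a full course.

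The one-year total is not exceeded in any of these cases.

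**The case against.** The strongest reply is that the ET draw looks deliberate. Section 8.7, footnote 7 and the ET column agree with one another. Table 3 omits ET for every tube, including haematology, which 8.11.1 expressly takes at ET. Its silence is therefore weak evidence that passive-transfer collection at ET was meant to be excluded. This stands: what the documents show is a missing ET volume and a collection listed in one place but not in the others.

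The serum may also have a use. Section 8.11.3 plans to transfer sera of differing titres, so an off-schedule sample could supply a titre. A subject who leaves on day 50 would give nearly the Visit 5 sample, and one who leaves on day 250 is about six months past the last large draw. This also stands. It argues against removing the collection from every ET visit, but not against a limit soon after a 200 ml draw.

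The 200 ml at ET is inferred from the rule together with 8.11.3, since no section states an ET volume. Section 8.11 leaves sampling detail to a Lab-Manual that is not among the documents. The inference is direct, but the protocol should not leave it to be made.

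A reader might also infer that the rule falls mainly on subjects who are unwell, or that pregnancy or a met stopping rule sets it off automatically. The documents do not support this. The reasons in 8.9 include withdrawn consent and non-compliance. Under 8.9.1, subjects barred from further vaccination stay in follow-up unless explicitly withdrawn, and a met study-level rule first leads to a safety review. Section 10.6 has pregnant subjects continue follow-up visits, and withdrawal under exclusion criterion 18 is optional in 8.9, although 17.1 leans towards withdrawal.

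**Conclusion.** The point holds, in a limited form. Followed as written, the plan can place two 200 ml research draws within days of each other: 508-540 ml in total for Visit 3 plus a prompt ET visit, and 470-490 ml for Visit 5 plus a prompt ET visit. The schedule's own windows never bring two such draws closer than 18 days.

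This rests on three assumptions: Table 3 volumes apply at ET; an ET visit after Visit 5 uses the Visit 7 set as 8.7 states; and the subject attends and consents to the draw. Because attendance is requested, the volumes are possible rather than certain. The documents give no basis for estimating how often it would happen.

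Three stronger conclusions might be drawn and should not be. The documents set no short-interval blood limit, so the figures do not show that a limit is breached, and no judgement is made here on whether the volume is clinically acceptable. The serum is not shown to be worthless. The planned total is not exceeded.

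**What to change.** Reconcile 8.7, Table 2 footnote 7 and its ET column with 8.11.3, Table 3 and the objective in 5.2, and carry the change into footnote 7 of SAP 1.6:

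- Omit the passive-transfer draw at an ET visit that falls less than 18 days after the previous 200 ml draw. This figure is the schedule's own shortest spacing and not a clinical threshold brought in from outside.
- List ET in 8.11.3 as a possible collection point for the remaining cases.
- Keep the ET safety laboratory, PRNT50, ELISA and PBMC samples as they are.
- Add the ET volumes to Table 3: 254-270 ml for the Visit 5 set and 216-220 ml for the Visit 7 set with passive transfer, or 54-70 ml and 16-20 ml without it.

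The cost is a clause in 8.7 and the footnotes, a qualifier on one cell of Table 2 and an addition to Table 3. A few sera that largely duplicate recently collected ones are lost. Subjects who leave long after their last large draw still contribute serum.

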8.8 Unscheduled Visits

Unscheduled visits can be conducted whenever deemed necessary. The extent of the examination performed at an unscheduled visit is at the discretion of the investigator. All procedures completed during an unscheduled visit should be documented in the source data and should also be entered to the electronic case report form (eCRF).

8.9 Discontinuation/Withdrawal of Subjects

Subjects may withdraw from participation in the study at any time. If a subject withdraws or is withdrawn prior to completion of the study, the reason for this decision should be recorded in the electronic case report forms (eCRFs) although it is recognised that the subject may refuse to provide a reason.

Generally, any enrolled/vaccinated subject may withdraw or be withdrawn from the study for the following reasons:

- The subject withdraws consent
- The subject fails to comply with the requirements of the protocol
- At the discretion of the investigator
- For an adverse event, which at the discretion of the investigator requires discontinuation of the subject or results in inability to continue to comply with trial procedures
- if the administration of a drug, which is not permitted by the study protocol, becomes necessary (this should be discussed and agreed between the investigator and the sponsor)
- violation of exclusion criteria 1, 4, 5, 7, 12, 15, 16, 17, 18, 19 or 20 during the study (this should be discussed and agreed between the investigator and the sponsor)

All subjects who withdraw or are withdrawn prematurely from the study will undergo an early termination visit (see section 8.7).

8.9.1 Safety Stopping Rules

Stopping rules are established at subject level and entire study level.

Individual Subjects Stopping Rules

The following are specific criteria for discontinuing individual subjects from further vaccination, but not from completing scheduled follow-up assessments, unless the subject is explicitly withdrawn from the study:

- Subjects who develop serious adverse reaction (SAR) at the discretion of the investigator
- Subjects who develop a potentially life-threatening (grade 4) solicited systemic adverse reaction that occurs without alternative etiology within 7 days after the study vaccination
- Subjects who develop a medical condition for which continued participation, in the opinion of the investigator, would pose a risk to the subject or would be likely to confound interpretation of the results
- Subjects who become pregnant during the treatment phase of the study
- Subjects who experience anaphylaxis within 24 hours or generalised urticaria within 72 hours after administration of the study vaccine

If any of these occur, appropriate measures to treat the subject will be taken and the sponsor or the sponsor designee will be notified immediately.

Entire Study Stopping Rules

The study will be stopped (no new enrolments and no additional vaccine administered) pending a safety review by the investigator and the sponsor, if any of the following occurs:

- One or more subjects experience a serious adverse reaction (SAR), based on the current reference safety information (Investigator's Brochure)
- One or more subjects' deaths assessed by the investigator, safety manager or sponsor as related to investigational product
- One or more subjects develop laryngospasm, bronchospasm or anaphylaxis within 24 hours of vaccine administration
- Three or more subjects develop injection-site ulceration, abscess or necrosis
- Three or more subjects experience generalised urticaria within 72 hours after administration of study product

Upon completion of this review, the sponsor will determine if study enrolment or treatment should be discontinued, or if study enrolment and treatment may continue according to the protocol.

Irrespective of the stopping rules the study may be temporarily suspended or prematurely terminated at any time if there is sufficient reasonable cause, and if agreed to by both the investigator and the sponsor as being in the best interests of subjects and justified on either medical or ethical grounds. In terminating the study, the sponsor, the CRO, and the investigator will ensure that adequate consideration is given to the protection of the subjects' interests.

Whenever the study is stopped the competent authorities and ethical committees will be informed.

In case the entire study has to be discontinued prematurely, all concerned subjects should be asked to perform an early termination visit.

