1. STUDY SYNOPSIS

Title of the Study	Observer blinded, randomised study to investigate safety, tolerability and long-term immunogenicity of different dose regimens and formulations of MV-CHIK in healthy volunteers
Study Centres	Celerion, [name]
Study Period	Study start, FSI Jun-2018
Study Phase	Clinical phase II
Objectives	
 – To investigate immunogenicity and safety of different MV-CHIK dose regimes, 28 days after one or two vaccinations – To investigate the immunogenicity and safety of a novel liquid vaccine formulation – To compare immunogenicity, safety and tolerability between different doses and formulations of MV-CHIK during a treatment period of 56 days – To evaluate the long-term immunogenicity of MV-CHIK up to one year after the first vaccination – To evaluate cellular responses induced by one or two immunisations – To collect human sera for efficacy evaluation, by passive transfer of anti-Chikungunya antibodies to virus susceptible non-human primates
Study Design	
Observer blinded, randomised immunogenicity and safety phase II trial in 60 healthy volunteer female and male subjects.
 
After completion of screening procedures, subjects will be randomised to one of five treatment groups (A, B, C, D or E):
 
A: 12 subjects will receive two low dose treatments with MV-CHIK 5×10^4 (± 0.5 log) TCID₅₀ /dose on day 0 and 28 (lyophilised formulation)
 
B: 12 subjects will receive two low dose treatments with MV-CHIK 1×10^5 (± 0.5 log) TCID₅₀ /dose on day 0 and 28 (liquid frozen formulation)
 
C: 12 subjects will receive two low dose treatments with MV-CHIK 1×10^5 (± 0.5 log) TCID₅₀ /dose on day 0 and 28 (liquid SPS® formulation)
 
D: 12 subjects will receive two high dose treatments with MV-CHIK 1×10^6 (± 0.5 log) TCID₅₀ /dose on day 0 and 28 (liquid frozen formulation)
 
E: 12 subjects will receive one high dose treatment with MV-CHIK 1×10^6 (± 0.5 log) TCID₅₀ /dose on day 0 (liquid frozen formulation) and placebo on day 28
 
After the screening visit, subjects will perform visits on study days 0, 14, 28, 42 and 56 for immunogenicity sample collection and safety follow up and additionally return to site on day 182 (6 months) and 365 (12 months) for long-term immunogenicity serum sampling.
 
Serum samples for passive transfer will be collected on days 0, 28, 56, 365.

Number of Subjects	60 healthy subjects

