8.11.4 Pregnancy Test – Contraception

Pregnancy will be determined by evaluation of β-HCG in serum at screening, Visit 1, 3 and 5 (or at early termination) for all women.

A woman is considered of childbearing potential (WOCBP), i.e. fertile, following menarche and until becoming post-menopausal unless permanently sterile. Permanent sterilization methods include hysterectomy, bilateral salpingectomy and bilateral oophorectomy.

A postmenopausal state is defined as no menses for 12 months without an alternative medical cause. A high follicle stimulating hormone (FSH) level in the postmenopausal range may be used to confirm a post-menopausal state in women not using hormonal contraception or hormonal replacement therapy. However, in the absence of 12 months of amenorrhea, a single FSH measurement is insufficient.

Only females with a negative result will be allowed to receive study vaccinations.

Subjects with a positive pregnancy test will be excluded from further treatments and the Investigator will inform the CRO immediately by completing a pregnancy report from. Please see section 10.6.

After the last IMP use (Day 56) all subjects will be follow up until Day 365.

Contraception

Birth control methods which may be considered as highly effective are those that can achieve a failure rate of less than 1% per year when used consistently and correctly are considered as highly effective birth control methods. Such methods include:

_ combined (estrogen and progestogen containing) hormonal contraception associated with inhibition of ovulation:

- Oral
- Intravaginal
- transdermal

_ progestogen-only hormonal contraception associated with inhibition of ovulation:

- oral
- injectable
- implantable

_ intrauterine device (IUD)

_ intrauterine hormone-releasing system (IUS)

_ bilateral tubal occlusion

_ vasectomised partner

_ sexual abstinence

Acceptable birth control methods which may not be considered as highly effective are those that result in a failure rate of more than 1% per year include:

_ progestogen-only oral hormonal contraception, where inhibition of ovulation is not the primary mode of action

_ male or female condom with or without spermicide

_ cap, diaphragm or sponge with spermicide

Birth control methods which are considered unacceptable include:

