17. DEVIATIONS FROM THE PROTOCOL

17.1 Relevant Protocol Deviations

A protocol deviation is any noncompliance with the clinical trial protocol, ICH GCP, manuals or local requirements. The noncompliance may be either on the part of the subject, the Investigator, or the study site staff. Consequently, corrective actions are to be developed and implemented promptly.

Important protocol deviations are deviations that might significantly affect the completeness, accuracy and/or reliability of the study data or that might significantly affect a subject's rights, safety or well-being.

Inclusion of subjects not satisfying the entry criteria will be subject to prior discussion with the sponsor and written approval from the sponsor. Subjects developing exclusion criteria during the study will be withdrawn, exceptions need prior discussion and written approval from the sponsor.

All protocol deviations will be listed in the study report and assessed as to their influence on the quality of the study analysis. No deviations from the protocol of any type will be made without complying with all the ethics committee's or regulatory authority's established procedures in accordance with applicable regulations.

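### Once a subject is known to be pregnant, the protocol still schedules the 200 ml passive-transfer draw, and section 17.1 conflicts with 8.9.1 on whether she stays in the study

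*Combined protocol and SAP*

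**What the plan says.** **Stopping and staying.** Protocol 8.9.1 lists pregnancy during the treatment phase among the criteria for "discontinuing individual subjects from further vaccination, but not from completing scheduled follow-up assessments, unless the subject is explicitly withdrawn from the study". Section 8.11.4 is limited in the same way: "Subjects with a positive pregnancy test will be excluded from further treatments". Section 10.6, on pregnancy reporting, expects her to keep attending follow-up visits and follows the pregnancy to its outcome.

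**Withdrawal.** Section 8.9 is permissive: "any enrolled/vaccinated subject may withdraw or be withdrawn from the study for the following reasons". One listed reason is "violation of exclusion criteria 1, 4, 5, 7, 12, 15, 16, 17, 18, 19 or 20 during the study", subject to discussion and agreement between investigator and sponsor. Criterion 18 in 7.3 covers a positive test during the treatment period. Section 17.1 is firmer: "Subjects developing exclusion criteria during the study will be withdrawn, exceptions need prior discussion and written approval from the sponsor".

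**The draw.** Under 8.11.3, "at Visit 3, 5 and 7, a volume of 200 ml blood will be collected for isolation of human serum". For early termination at or before Visit 5, 8.7 says "subjects shall perform all procedures as defined for Visit 5"; after Visit 5, the Visit 7 procedures apply. The passive-transfer row of Table 2 is marked in the early termination column.

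**Use of the serum.** Collecting it is a secondary objective (5.2). No endpoint in 6.2 uses it, and SAP 5.2 says that the analysis of passive-transfer results is outside the SAP.

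**The concern.** The protocol tests for pregnancy at screening and at Visits 1, 3 and 5, so it foresees this case, and it says clearly that vaccination stops. It does not say what happens to the largest blood draw in the schedule. Followed as written, both staying and leaving lead to 200 ml being taken, for a purpose outside the trial's endpoints, from someone the site knows is pregnant.

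The second issue is the default. If nobody takes a decision, 8.9.1 keeps her in follow-up and 17.1 takes her out. The choice affects her remaining visits and whether her later titres appear in the by-visit tables, because SAP section 5 only lists early termination samples.

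**Working it through.** **1. Reproduce the plan's blood volume (Table 3, ml).** Pregnancy test 3-5, haematology 9-15, coagulation 9-15, chemistry 24-30, PRNT50 40-50, Chikungunya ELISA 40-50, PBMC 120-150, passive transfer 650.
- Low: 3 + 9 + 9 + 24 + 40 + 40 + 120 + 650 = 895
- High: 5 + 15 + 15 + 30 + 50 + 50 + 150 + 650 = 965

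Both match the stated 895-965 ml.

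**2. Visit 5, or early termination at or before Visit 5.**
- Without passive transfer: haematology 3-5 + coagulation 3-5 + chemistry 8-10 + PRNT50 8-10 + ELISA 8-10 + PBMC 24-30 = 54-70 ml
- With it: 254-270 ml
- Share: 200/270 = 74% to 200/254 = 79%

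Every endpoint and safety sample at that visit fits in the 54-70 ml.

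**3. The routes to the draw.**

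| Route | Sections | 200 ml draw |
|---|---|---|
| Stays | 8.9.1, 8.5.5, 8.11.3 | Visit 5, and Visit 7 if still pregnant |
| Withdrawn at or before Visit 5 | 8.9, 8.7, Table 2 | early termination (Visit 5 procedures) |
| Withdrawn after Visit 5 | 8.9, 8.7, Table 2 | early termination (Visit 7 procedures) |

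The follow-up in 8.9.1 could be read as Visits 6 and 7 only. The synopsis uses the word for the treatment period too ("subjects will perform visits on study days 0, 14, 28, 42 and 56 for immunogenicity sample collection and safety follow up"), and on the narrow reading the early termination route remains.

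Visit 7 is a secondary matter. Assuming a 266-day gestation, a pregnancy begun by day 56 ends by about day 56 + 266 = 322, before the Visit 7 window opens on day 365 - 14 = 351. A draw in pregnancy at Visit 7 would therefore mainly concern pregnancies begun after the treatment phase, which 8.9.1 does not address.

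**4. The defaults compared.**

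| Section | If no decision is taken |
|---|---|
| 8.9.1 (names pregnancy) | stays, no more vaccine |
| 8.11.4, 10.6 (pregnancy sections) | consistent with staying |
| 8.9 (criterion 18) | sets no default |
| 17.1 (any exclusion criterion) | withdrawn |

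**5. How often.** The documents give neither the number of women nor a detection lag. Assumed: 20-40 women, 1-5% contraceptive failure per year, and 14 days from conception to detection. Expected number = women × annual rate × days at risk / 365.
- Found by the Visit 3 test (conception by day 14): 20 × 0.01 × 14/365 = 0.008 to 40 × 0.05 × 14/365 = 0.08
- Known by any route before Visit 5 (conception by day 42): 20 × 0.01 × 42/365 = 0.02 to 40 × 0.05 × 42/365 = 0.23

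The second range counts every such pregnancy as found by a scheduled, unscheduled or self test, so it is an upper bound for these inputs.

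**6. Reach into the primary analysis.** A primary titre could be lost mainly for a Group A-D subject who has had dose 2 and is withdrawn before Visit 5. With 48/60 = 0.8 of the women in Groups A-D and conception between about day 14 and day 42:
- 20 × 0.8 × 0.01 × 28/365 = 0.01 to 40 × 0.8 × 0.05 × 28/365 = 0.12

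Each would be 1 of 12 (8.3%) in one group. In Group E the primary titre is Day 28, so later withdrawal does not change it. If pregnancy is found before dose 2, a Group A-D subject misses that dose, which SAP 2.9 lists as a major deviation.

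**The case against.** **The default is largely settled.** Section 8.9.1 names pregnancy, and 8.11.4 and 10.6 fit with it. Section 17.1 is a general deviations clause with an exception route, and the sponsor is notified under 8.9.1 in any case. Much of this stands. A reader might infer three competing rules; the documents do not support that, because 8.9 says only that she may be withdrawn and can be read together with 8.9.1. What remains is one conflict, between 8.9.1 and 17.1, and neither section says which governs.

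**The draw serves a stated objective, and nobody is compelled to give it.** Serum collection is in 5.2 with a rationale in 4.5, a subject may withdraw at any time, and the investigator has discretion. The Lab-Manual was not supplied and the consent pages were removed, so an exemption there cannot be excluded. This stands as a limit: the gap is in the protocol text available. It does not explain why a case the protocol tests for should depend on refusal or discretion.

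**No harm is shown.** A reader might infer that the plan endangers pregnant subjects. The documents give no volume limit in pregnancy and no evidence that 200 ml is harmful, so the point is one of avoidable burden.

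**The case is rare and the remedy partial.** At Visits 3 and 5 the pregnancy test uses the same-day chemistry sample, so a pregnancy first found there may come to light after the 200 ml is taken. This is correct, and it keeps the point minor.

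**Conclusion.** The point holds as a minor one. The protocol's own rules schedule a 200 ml passive-transfer draw for a subject known to be pregnant, whether she stays or is withdrawn, and no section supplied waives it. The draw is 74-79% of the Visit 5 volume and feeds no endpoint or SAP analysis. Section 17.1 also conflicts with 8.9.1 on whether she stays.

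The frequency, 0.02-0.23 known pregnancies before Visit 5, rests entirely on the assumed number of women, failure rate and detection lag. The volumes rest on Table 3 alone.

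A reader might also infer that the primary per-protocol result is at risk. The documents do not support that. The expected number is 0.01-0.12, it requires detection outside the scheduled tests and withdrawal before Visit 5, and she might be excluded anyway: SAP 2.9 leaves other deviations that could affect immune response to blinded case-by-case decisions. No material effect on the primary analysis is claimed.

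**What to change.** - In 8.7 and 8.9.1, and in a footnote to the passive-transfer row of Table 2, state that this draw is not taken while a subject is known to be pregnant, and that all other scheduled samples (PRNT50, ELISA, PBMC, safety) and pregnancy follow-up continue.
- In 17.1, add that for criterion 18 after the first dose, 8.9.1 governs: vaccination stops and she stays in follow-up unless she chooses, or the investigator and sponsor decide, otherwise.

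Section 8.9 needs no change, and no reordering of procedures at Visit 3 or Visit 5 is proposed.

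The cost is three short additions and one footnote. There is no extra venepuncture, and the waiver alters no endpoint or results table; Listing 2.3.5 in SAP 7.2 already has a field for why a sample was not taken. The downside is a small loss to the collection objective. Of 60 × 3 = 180 planned 200 ml lots, one would be forgone per case (1/180 = 0.6%), rarely two (2/180 = 1.1%), for example when pregnancy is already known before the Visit 3 draw.
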